7.2 Pembrolizumab

Pembrolizumab dose interruption for subjects who experience pembrolizumab-related toxicity will be in accordance with the table below. Adverse events (both nonserious and serious) associated with pembrolizumab exposure, including coadministration with additional compounds, may represent an immunologic etiology. These AEs may occur shortly after the first dose or several months after the last dose of treatment. Pembrolizumab must be withheld for drug-related toxicities and severe or life-threatening AEs as per the table below.

Dose Modification and Toxicity Management Guidelines for Immune-related Adverse Events Associated with Pembrolizumab and Combination Therapy

General instructions: 
 1. Corticosteroid taper should be initiated upon AE improving to Grade 0 or 1 and continue to taper over at least 4 weeks. 2. For situations where pembrolizumab has been withheld, pembrolizumab can be resumed after AE has improved to Grade 0 or 1 and corticosteroid has been tapered. Pembrolizumab should be permanently discontinued if AE does not resolve within 12 weeks of last dose or corticosteroids cannot be reduced to ≤ 10 mg prednisone or equivalent per day within 12 weeks. 				
*For severe and life-threatening irAEs, IV corticosteroid should be initiated first followed by oral steroid. Other immunosuppressive treatment should be initiated if irAEs cannot be controlled by corticosteroids.				
Immune-related Adverse Event	Toxicity Grade or Conditions (CTCAE V5.0)	Action Taken with Pembrolizumab	irAE Management with Corticosteroids and Other Therapies	Monitor and Follow-up
Pneumonitis	Grade 2	Withhold	Administer corticosteroids (initial dose of 1-2 mg/kg prednisone or equivalent) followed by taper. Add prophylactic antibiotics for opportunistic infections.	Monitor subjects for signs and symptoms of pneumonitis. Evaluate subjects with suspected pneumonitis with radiographic imaging and initiate corticosteroid treatment.
	Grade 3 or 4, or recurrent Grade 2	Permanently discontinue		

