Diarrhea / Colitis	Grade 2 or 3	Withhold	Administer corticosteroids (initial dose of 1-2 mg/kg prednisone or equivalent) followed by taper. Subjects with diarrhea/ colitis should be advised to drink liberal quantities of clear fluids. If sufficient oral fluid intake is not feasible, fluid and electrolytes should be substituted via IV infusion.	Monitor subjects for signs and symptoms of enterocolitis (i.e., diarrhea, abdominal pain, blood or mucus in stool with or without fever) and of bowel perforation (i.e., peritoneal signs and ileus). Subjects with Grade ≥ 2 diarrhea suspecting colitis should consider GI consultation and performing endoscopy to rule out colitis
	Grade 4 or recurrent Grade 3	Permanently discontinue		
AST / ALT elevation or Increased bilirubin	Grade 2 ^a	Withhold	Administer corticosteroids (initial dose of 0.5 - 1 mg/kg prednisone or equivalent) followed by taper.	Monitor with liver function tests (consider weekly or more frequently until liver enzyme value returned to baseline or is stable)
	Grade 3 ^b or 4 ^c	Permanently discontinue	Administer corticosteroids (initial dose of 1-2 mg/kg prednisone or equivalent) followed by taper.	

Type 1 diabetes mellitus (T1DM) or Hyperglycemia	Newly onset T1DM or Grade 3 or 4 hyperglycemia associated with evidence of β -cell failure	Withhold ^d	Initiate insulin replacement therapy for subjects with T1DM. Administer antihyperglycemic in subjects with hyperglycemia.	Monitor subjects for hyperglycemia or other signs and symptoms of diabetes.
Hypophysitis	Grade 2	Withhold	Administer corticosteroids and initiate hormonal replacements as clinically indicated.	Monitor for signs and symptoms of hypophysitis (including hypopituitarism and adrenal insufficiency).
	Grade 3 or 4	Withhold or permanently discontinue ^d		
Hyperthyroidism	Grade 2	Continue	Treat with nonselective beta-blockers (eg, propranolol) or thionamides as appropriate.	Monitor for signs and symptoms of thyroid disorders.
	Grade 3 or 4	Withhold or permanently discontinue ^d		
Hypothyroidism	Grade 2-4	Continue	Initiate thyroid replacement hormones (eg, levothyroxine or liothyroinine) per standard of care.	Monitor for signs and symptoms of thyroid disorders.
Nephritis: grading according to increased creatinine or acute kidney injury	Grade 2	Withhold	Administer corticosteroids (prednisone 1-2 mg/kg or equivalent) followed by taper.	Monitor changes of renal function.
	Grade 3 or 4	Permanently discontinue		

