Neurological Toxicities	Grade 2	Withhold	Based on severity of AE administer corticosteroids	Ensure adequate evaluation to confirm etiology and/or exclude other causes
	Grade 3 or 4	Permanently discontinue		
Myocarditis	Grade 1	Withhold	Based on severity of AE administer corticosteroids.	Ensure adequate evaluation to confirm etiology and/or exclude other causes
	Grade 2, 3 or 4	Permanently discontinue		

Exfoliative Dermatologic Conditions	Suspected SJS, TEN, or DRESS	Withhold	Based on severity of AE administer corticosteroids	Ensure adequate evaluation to confirm etiology or exclude other causes
	Confirmed SJS, TEN, or DRESS	Permanently discontinue		
All other irAEs	Persistent Grade 2	Withhold	Based on type and severity of AE administer corticosteroids.	Ensure adequate evaluation to confirm etiology and/or exclude other causes.
	Grade 3	Withhold or discontinue based on the type of event ^e		
	Grade 4 or recurrent Grade 3	Permanently discontinue		

AE(s)=adverse event(s); ALT= alanine aminotransferase; AST=aspartate aminotransferase; CTCAE=Common Terminology Criteria for Adverse Events; DRESS=Drug Rash with Eosinophilia and Systemic Symptom; GI=gastrointestinal; IO=immuno-oncology; ir=immune related; IV=intravenous; SJS=Stevens-Johnson Syndrome; T1DM=type 1 diabetes mellitus; TEN=Toxic Epidermal Necrolysis; ULN=upper limit of normal.

Note: Non-irAE will be managed as appropriate, following clinical practice recommendations.

a AST/ALT: >3.0 to 5.0 x ULN if baseline normal; >3.0 to 5.0 x baseline, if baseline abnormal; bilirubin:>1.5 to 3.0 x ULN if baseline normal; >1.5 to 3.0 x baseline if baseline abnormal

b AST/ALT: >5.0 to 20.0 x ULN, if baseline normal; >5.0 to 20.0 x baseline, if baseline abnormal; bilirubin:>3.0 to 10.0 x ULN if baseline normal; >3.0 to 10.0 x baseline if baseline abnormal

c AST/ALT: >20.0 x ULN, if baseline normal; >20.0 x baseline, if baseline abnormal; bilirubin: >10.0 x ULN if baseline normal; >10.0 x baseline if baseline abnormal

d The decision to withhold or permanently discontinue pembrolizumab is at the discretion of the investigator or treating physician. If control achieved or ≤ Grade 2, pembrolizumab may be resumed.

e Events that require discontinuation include but are not limited to: encephalitis, and other clinically important irAEs (eg, vasculitis and sclerosing cholangitis)

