7.2.2 Combination Therapy with Pembrolizumab

Attribution of Toxicity: When study interventions are administered in combination, attribution of an adverse event to a single component is likely to be difficult. Therefore, while the investigator may attribute a toxicity event to the combination, to lenvatinib alone or to pembrolizumab alone, for adverse events listed in the table in Section 7.2 above, both interventions must be held.

Restarting Study Interventions:

Participants may not have any dose modifications (no change in dose or schedule) of pembrolizumab in this study, as described in the table in Section 7.2 above. If pembrolizumab is to be held for a related toxicity, the dose will be skipped and restarted at the next cycle if resolved.

- If the toxicity does not resolve or the criteria for resuming treatment are not met, the participant must be discontinued from all study interventions, unless the toxicity can be clearly attributed to only one of the study therapies.
- If the toxicities do resolve and conditions are aligned with what is defined in the table in Section 7.2 above, the combination of lenvatinib and pembrolizumab may be restarted at the discretion of the investigator. In these cases where the toxicity is attributed to the combination or to lenvatinib alone, re-initiation of pembrolizumab as a monotherapy may be considered at the principal investigator's discretion.

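### Section 7.2.2 orders both drugs held for events in the Section 7.2 table, yet two of that table's 23 rows say to continue pembrolizumab

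*Combined protocol and SAP*

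**What the plan says.** Four parts of the combined protocol and SAP bear on this point.

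- **Section 7.0** lets the two drugs be held independently when a toxicity is clearly due to one of them, but takes toxicities covered by Section 7.2 out of that permission.
- **Section 7.2** ties withholding to its table: "Pembrolizumab must be withheld for drug-related toxicities and severe or life-threatening AEs as per the table below". The table is headed "Dose Modification and Toxicity Management Guidelines for Immune-related Adverse Events Associated with Pembrolizumab and Combination Therapy", so it is meant for the combination as well as for pembrolizumab alone. For hypothyroidism Grade 2-4 the action is Continue, with the management "Initiate thyroid replacement hormones (eg, levothyroxine or liothyroinine) per standard of care". For hyperthyroidism Grade 2 the action is also Continue, with "Treat with nonselective beta-blockers (eg, propranolol) or thionamides as appropriate". Footnote d, attached to hyperthyroidism Grade 3 or 4 among other rows, adds "If control achieved or ≤ Grade 2, pembrolizumab may be resumed".
- **Section 7.2.2** states that whether the investigator blames the combination, lenvatinib or pembrolizumab, "for adverse events listed in the table in Section 7.2 above, both interventions must be held".
- **Section 7.1**, footnote b to the lenvatinib table, puts optimal medical management of hypothyroidism ahead of any interruption or reduction of lenvatinib. The same table leaves lenvatinib unchanged for tolerable Grade 2 toxicity.

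**The concern.** The trigger in 7.2.2 is that an event is listed in the table. The two thyroid rows are listed, so 7.2.2 requires a hold where the table says to carry on. Both instructions are addressed to the same investigator about the same drug and the same event.

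Read literally, 7.2.2 stops both drugs for events that the table manages with hormone replacement, beta-blockers or thionamides. A hold then brings the general instructions of the table into play: "pembrolizumab can be resumed after AE has improved to Grade 0 or 1 and corticosteroid has been tapered", and "Pembrolizumab should be permanently discontinued if AE does not resolve within 12 weeks of last dose". Under the restart rules of 7.2.2, failure to meet the resumption criteria ends all study treatment unless the toxicity is clearly due to one drug, and 7.2.2 itself says such attribution is likely to be difficult. A patient with persistent hypothyroidism on replacement could in principle lose both drugs by this route.

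The more likely consequence is uneven practice. One site follows the event-specific row and treats through; another follows the combination rule and holds. Four sites are planned, and protocol adherence is an audit item in Section 14.0, so either choice departs from one written instruction. Avoidable holds also reduce delivered dose, which bears on the 80% dosage criterion for the per-protocol set in Section 15.5.

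**Working it through.** The plan states no figure on this point, so the check is a reading of the table, a row count and a bound on exposure.

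**1. Row count.** Rows (grade or condition) per event in the Section 7.2 table:

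| Event | Rows | Rows saying Continue |
|---|---|---|
| Pneumonitis | 2 | 0 |
| Diarrhea / colitis | 2 | 0 |
| AST / ALT / bilirubin | 2 | 0 |
| T1DM / hyperglycemia | 1 | 0 |
| Hypophysitis | 2 | 0 |
| Hyperthyroidism | 2 | 1 (Grade 2) |
| Hypothyroidism | 1 | 1 (Grade 2-4) |
| Nephritis | 2 | 0 |
| Neurological | 2 | 0 |
| Myocarditis | 2 | 0 |
| Exfoliative dermatologic | 2 | 0 |
| All other irAEs | 3 | 0 |
| **Total** | **23** | **2** |

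By action: 10 withhold + 8 permanently discontinue + 3 either of these + 2 continue = 23. The conflict touches 2/23 = 8.7% of rows. The remaining 21 already stop pembrolizumab, so a joint hold does not contradict them.

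**2. Is an exception written anywhere?**

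- Section 7.0 does not supply one. Its carve-out removes independent holds for Section 7.2 toxicities and so sends the reader to 7.2.2.
- Section 6.3.3 limits the treatment guidance to events related to pembrolizumab. It does not override a rule that applies under any attribution, and the conflict remains for pembrolizumab-related thyroid events.
- Section 7.2 makes withholding follow the table. This shows intent but does not qualify the later sentence in 7.2.2.
- Footnote d points the same way. If pembrolizumab may restart once Grade 3 or 4 hyperthyroidism has fallen to Grade 2 or below, a compulsory hold at Grade 2 makes no sense.
- Footnote b in Section 7.1 is a further clash, on the lenvatinib side: it calls for medical management of hypothyroidism first, whereas 7.2.2 calls for a hold.

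**3. How far the consequence runs.** For hypothyroidism, a literal hold leads to the Grade 0 or 1 resumption rule and the 12-week limit. For hyperthyroidism the chain is weaker, because footnote d shows that the protocol accepts pembrolizumab at Grade 2.

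**4. How many patients could have the event.** Section 2.5 reports hypothyroidism in 67% of 30 clear cell patients on this combination, about 20 patients (0.67 × 30 = 20.1), with no grade split and no attribution. Assume that rate applies to the 34 planned patients:

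- upper limit, if every case were Grade 2-4: 0.67 × 34 = 22.8, about 23 patients;
- lower limit, if every case were Grade 1: 0 patients.

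The documents give no rate for hyperthyroidism.

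**5. Effect on the design.** The Simon design's figures depend only on the response rates, stage sizes and cut-offs. Summing over stage 1 responders x = 2 to 9, P(X₁ = x; n = 9) × P(X₂ ≥ 9 − x; n = 25) gives 0.0474 at a 15% response rate and 0.8107 at 35%. These match the stated 0.047 and 0.811 in Section 15.4. The hold rule does not enter this calculation.

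**The case against.** The best defence is that 7.2.2 is about which drugs to hold, not whether to hold. The sentence sits under a heading on attribution and follows from the difficulty of blaming one drug. The next paragraph speaks conditionally of pembrolizumab being held, and restarting is tied back to the table. Reading 7.2.2 with no qualifier at all would even catch Grade 1 events that have no row. If the grade column is allowed to limit the sentence, the action column beside it can limit it too, and the conflict disappears. Footnote b in Section 7.1 also makes the intent plainer for hypothyroidism.

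The defence adds that loss of all treatment requires several unlikely steps, including applying a resumption rule built around a corticosteroid taper to a condition managed without steroids. It also notes that 0 to 23 is a very wide range, borrowed from a clear cell cohort of whom 60% had prior therapy, and that it counts patients with the event, not patients mishandled.

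Much of this stands. The defence's reading is very probably what the authors meant, the route to full discontinuation is a possibility and not a forecast, and the range is only a bound. What does not stand is the conclusion that no change is needed. The rule is mandatory, it governs dosing, and the limiting words are absent. That a stricter literal reading would also catch Grade 1 events shows that the sentence is too broad, not that it is clear. The suggestion that Section 7.0 can be left alone also fails: its carve-out would still bar lenvatinib from following Section 7.1 independently for these thyroid events.

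**Conclusion.** The inconsistency is real and should be corrected. Two of 23 rows, hypothyroidism Grade 2-4 and hyperthyroidism Grade 2, carry opposite instructions for pembrolizumab, and nothing in the protocol reconciles them. This conclusion rests on the text alone and is firm.

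The number of patients involved is not known. The range of 0 to about 23 of 34 for Grade 2-4 hypothyroidism assumes that the any-grade rate from the clear cell study carries over to this population, and its upper end assumes that every case reaches at least Grade 2. The practical risk is uneven handling across sites and some avoidable interruption of treatment. Sample size, stopping rule and primary test are untouched.

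**What to change.** Replace the sentence in 7.2.2 with wording to this effect:

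> Whatever the attribution, lenvatinib and pembrolizumab are held together for those events and grades at which the Section 7.2 table requires pembrolizumab to be withheld or permanently discontinued. Where the table says Continue, pembrolizumab continues and lenvatinib follows the Section 7.1 table.

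Add a matching phrase to Section 7.0, so that its exception covers only toxicities for which the Section 7.2 table requires withholding or discontinuation.

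The cost is protocol wording only: one sentence and one phrase. The 21 other rows, the sample size and the analysis stay as they are.

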8.0 REGULATORY AND REPORTING REQUIREMENTS

The entities providing oversight of safety and compliance with the protocol require reporting as outlined below. Please refer to Appendix C for definitions and Appendix D for a grid of reporting timelines.

Adverse events will be tracked from start of treatment through 120 days after last day of study treatment. All adverse events must be recorded on the toxicity tracking case report form (CRF) with the exception of:

- Baseline adverse events, which shall be recorded on the medical history CRF

Refer to the data submission schedule in Section 11 for instructions on the collection of AEs in the EDC.

Reporting requirements for Washington University study team may be found in Section 8.1. Reporting requirements for secondary site study teams participating in Washington University-coordinated research may be found in Section 8.2.

8.1 Washington University PI Reporting Requirements

8.1.1 Reporting to the Human Research Protection Office (HRPO) at Washington University

Reporting will be conducted in accordance with Washington University IRB Policies.

Pre-approval of all protocol exceptions must be obtained prior to implementing the change.

8.1.2 Reporting to the Quality Assurance and Safety Monitoring Committee (QASMC) at Washington University

The Washington University PI (or designee) is required to notify the QASMC of any unanticipated problems involving risks to participants or others occurring at WU or any BJH or SLCH institution that has been reported to and acknowledged by HRPO. (Unanticipated problems reported to HRPO and withdrawn during the review process need not be reported to QASMC.)

QASMC must be notified within **10 days** of receipt of IRB acknowledgment via email to [contact]. Submission to QASMC must include the myIRB form and any supporting documentation sent with the form.

For events that occur at secondary sites, the Washington University PI (or designee) is required to notify the QASMC within 10 days of Washington University notification via email to [contact]. Submission to QASMC must include either the myIRB form and supporting documentation or (if not submitted to myIRB) the date of occurrence, description of the event, whether the event is described in the currently IRB approved materials, the event outcome, determination of relatedness, whether currently enrolled participants will be notified, and whether the informed consent document and/or any study procedures will be modified as a result of this event.

8.1.3 Reporting to Merck

8.1.3.1 Overdose

If an adverse event(s) is associated with (“results from”) the overdose of a Merck product (either pembrolizumab or lenvatinib), the adverse event(s) is reported as a serious adverse event, even if no other seriousness criteria are met.

If a dose of Merck’s product meeting the protocol definition of overdose is taken without any associated clinical symptoms or abnormal laboratory results, the overdose is reported as a non-serious Event of Clinical Interest

(ECI), using the terminology “accidental or intentional overdose without adverse effect.”

All reports of overdose with and without an adverse event must be reported within 24 hours to the Washington University PI and within 2 working days to Merck Global Safety. (Attn: Worldwide Product Safety; [contact])

8.1.3.2 Pregnancy and Lactation

Although pregnancy and infant exposure during breastfeeding are not considered adverse events, it is the responsibility of investigators or their designees to report any pregnancy or lactation in a subject (spontaneously reported to them) that occurs during the study.

Pregnancies and infant exposures during breastfeeding that occur after the consent form is signed but before treatment allocation/randomization must be reported by the investigator if they cause the participant to be excluded from the trial, or are the result of a protocol-specified intervention, including but not limited to washout or discontinuation of usual therapy, diet, placebo treatment or a procedure.

Pregnancies and infant exposures during breastfeeding that occur from the time of treatment allocation/randomization through 120 days following cessation of Sponsor’s product, or 30 days following cessation of treatment if the participant initiates new anticancer therapy, whichever is earlier, must be reported by the investigator. All reported pregnancies must be followed to the completion/termination of the pregnancy. Pregnancy outcomes of spontaneous abortion, missed abortion, benign hydatidiform mole, blighted ovum, fetal death, intrauterine death, miscarriage and stillbirth must be reported as serious events (Important Medical Events). If the pregnancy continues to term, the outcome (health of infant) must also be reported.

Such events must be reported within 24 hours to the Washington University PI and within 2 working days to Merck Global Safety. (Attn: Worldwide Product Safety; [contact])

8.1.3.3 Serious Adverse Events

For the time period beginning when the consent form is signed until treatment allocation/randomization, any serious adverse event, or follow up to a serious adverse event, including death due to any cause that occurs to any participant must be reported within 24 hours to the Washington University PI and within 2 working days to Merck Global Safety if it causes the participant to be excluded from the trial, or is the result of a protocol-specified intervention, including but not limited to washout or

discontinuation of usual therapy, diet, placebo treatment or a procedure.

For the time period beginning at treatment allocation/randomization through 90 days following cessation of treatment, or 30 days following cessation of treatment if the participant initiates new anticancer therapy, whichever is earlier, any serious adverse event, or follow up to a serious adverse event, including death due to any cause whether or not related to the Merck product, must be reported within 24 hours to the Washington University PI and within 2 working days to Merck Global Safety.

Additionally, any serious adverse event, considered by an investigator who is a qualified physician to be related to Merck product that is brought to the attention of the investigator at any time following consent through the end of the specified safety follow-up period specified in the paragraph above, or at any time outside of the time period specified in the previous paragraph also must be reported immediately to Merck Global Safety.

SAE reports and any other relevant safety information are to be forwarded to the Merck Global Safety [contact]

A copy of all 15 Day Reports and Annual Progress Reports is submitted as required by FDA, European Union (EU), Pharmaceutical and Medical Devices agency (PMDA) or other local regulators. Investigators will cross reference this submission according to local regulations to the Merck Investigational Compound Number (IND, CSA, etc.) at the time of submission. Additionally investigators will submit a copy of these reports to Merck & Co., Inc. (Attn: Worldwide Product Safety; [contact]) at the time of submission to FDA.

